ATTACHMENT A. Pre-Screen Checklist

**Calorie Restriction Checklist – Inclusion and Exclusion Criteria
(partial)**

INCLUSION CRITERIA

- BMI \geq 27; weight \leq 350 lbs
- Age of 55-70 years

EXCLUSION CRITERIA

- History of cardiovascular disease
- History of cerebrovascular or other neurological diseases
- History of substance abuse in the past 6 months or positive urine drug screen
- History of clinically significant endocrine disorders (e.g. hypothyroidism)
- History of eating disorders, significant GI disorders or malabsorption disorders
- History of type 2 diabetes and/or use of anti-diabetes medications or insulin;
- History of hypoglycemia
- Current use of systemic corticosteroids
- Chronic HIV, HCV or HBV infections
- Current use of immunosuppressive agents (any)
- Contraindications for MRI (pacemakers, ferrous metal implants or shrapnel in or around the head, etc.)
- Contraindications to LP, such as Coumadin, known coagulopathy. Aspirin 81 mg qd is allowed. Aspirin up to 325 mg qd is allowed, if withheld for 7 days prior to the LP.
- Pregnancy or nursing.

ATTACHMENT B. ADVERTISEMENT BROCHURE AND FLIER

Recruitment materials are available as separate documents.

ATTACHMENT C. Activity Log

Activity Log (Week X)

Instructions: For each day you wear the physical activity bracelet, please write down the times when you woke up, bathed, exercised, and went to bed. If one of these activities did not occur, you can leave it blank.

Day 1

Woke up: _____
Bathed: _____
Exercised: _____
Went to bed: _____

Day 2

Woke up: _____
Bathed: _____
Exercised: _____
Went to bed: _____

Day 3

Woke up: _____
Bathed: _____
Exercised: _____
Went to bed: _____

Day 4

Woke up: _____
Bathed: _____
Exercised: _____
Went to bed: _____

ATTACHMENT D. PANAS

Positive and Negative Affective Schedule (PANAS)

Intermittent Calorie Restriction

Instruction: "Do you feel this way right now?"

	Very slightly or not at all	A little	Moderately	Quite a Bit	Extremely
Interested					
Distressed					
Excited					
Upset					
Strong					
Guilty					
Scared					
Hostile					
Enthusiastic					
Proud					
Irritable					
Alert					
Ashamed					
Inspired					
Nervous					
Determined					
Attentive					
Jittery					
Active					
Afraid					

Participant ID: _____
Investigator/Staff Name: _____

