Cognition and affect: Moderate CR has profoundly beneficial effects on memory, such as the California Verbal Learning Test (CVLT), in sedentary aged adults at risk for AD,⁶⁵ an effect that may be associated with insulin resistance. Consequently, we will assess verbal memory for unstructured information with the CVLT, as well as structured information with Logical Memory I and II; these tests are common neuropsychological measures. Memory recall generally begins to decline starting in the fifth decade of life,⁶⁶ while peripheral IR may be related to subclinical declines in memory performance within the range of normal variability, but also subclinical hippocampal microstructural changes.^{67,68} In addition, higher IR in older adults predicts executive function deficits in Trails A and B⁶⁹, as well as the Symbol Digit Modalities Test and Stroop Color-Naming task.⁷⁰ We intend to measure executive function using the newly developed computerized assessment tool called “Examiner” (<http://examiner.ucsf.edu/>). This software reliably and validly assesses domains of executive function and is intended to become the “gold standard” for clinical trials. We hypothesize that participants on 8 weeks of 5-2 CR will show better performance on executive function and memory tasks compared to baseline and controls, within the normal range.

Regarding secondary measures specific to cognition, we screen out subjects with subclinical cognitive dysfunction by using the Mini Mental State Exam (MMSE) and an inclusive cut-off of 26 out of 30. Given the possibility of psychological stress associated with the two diets, we will gauge mood using the Positive and Negative Affect Schedule, or PANAS⁷¹ and the general quality of life of participants using the RAND Health 36-Item Short Form Health Survey (RAND SF-36) as previously described.⁴⁰ These questionnaires use Likert scales that assess mood, level of energy, difficulty concentrating, headaches, feeling cold, constipation, specific negative emotions (depression, anxiety, and

irritability), hunger and preoccupation with food. We hypothesize that participants on 8 weeks of 5-2 CR will show improved positive over negative affect and general quality of life compared to controls.

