The study is comprised of: an initial telephone pre-screening to describe the study and inclusion/exclusion criteria to potential participants; a "Screening Visit"; randomization into one of two groups; a "Baseline Visit"; the "Outcome Visit" after 8 weeks. During the 8-week period for the 5-2 CR or control groups, participants will return every two weeks for "Compliance Visits", to assess and reinforce dietary compliance in keeping with previous protocols.^{39,40,94} The Outcome Visit will take place at the conclusion of the 8-week phase. Specifically for the 5-2 CR group, the Outcome Visit will be timed during the second of the two CR days. In total, there will be 6 outpatient visits to the NIA Clinical Unit: Screening Visit, Baseline Visit, Week 2 Compliance Visit, Week 4 Compliance Visit, Week 6 Compliance Visit, and the Week 8 Outcome Visit. There will be an additional follow-up phone call or electronic mail within 3 days of completing the Week 8 Visit to assess any problems related to their final visit. Accelerometry will be implemented on two occasions for 96 hours each time: once between the screening and baseline visits and again after the Week 8 Outcome Visit. Throughout the study, additional safety visits may take place for any clinically significant. Participants will be involved in the study for approximately 8 – 11 weeks (allowing for an up to 3 week gap between Screening and Baseline Visits). Study participation will end with completion of accelerometry after the Week 8 Outcome Visit.

It is anticipated that participants in this study will occasionally miss or fail to complete an assessment or procedure, such as a completion of a rating scale or a blood draw. Omissions such as these will be considered expected events and not protocol deviations provided they are infrequent and do not include data needed to assess safety or the primary study outcome. Cumulative proportions of these missed events in the study population will be presented to the IRB annually. In addition, the rate of omissions will be monitored by the Investigators. If an individual misses more than 15% of the required assessments/procedures or if more than 15% of the participants miss completion of the same assessment or procedure, it will be considered a deviation and a deviation report

will be sent to the IRB within two weeks.

Table 1: Procedures

Procedures	Visit 1	Visit 2		Visit 3, 4, 5	Visit 6	
		Week 0		Weeks 2, 4, 6	Week 8	

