	1 Day 3-hours	Day 1 7-9 hours	Day 2 optional	1 Day 1-hour	Day 1 7-9 hours	Day 2 optional
Procedures	Screening	Baseline		Compliance (Outpatient)	Outcome	
Informed Consent	X					
History and Physical (MMSE Visit 1 only)	X				X	
Review Inclusion/Exclusion Criteria	X	X				
Symptoms Review Questionnaire	X	X			X	
PANAS, RAND SF-36		X		X	X	
Cognitive Testing		X			X	
MRI		X			X	
Accelerometers	X				X	
Vital Signs	X	X		X	X	
Anthropometric measurements	X	X		X	X	
Urine Drug Screen	X					
Urine Pregnancy test	X	X			X	
Fasting Blood Draw	X	X		X	X	
Mixed Meal Tolerance Test		X			X	
Lumbar Puncture		X			X	
Dispense Diet Shakes (5-2 CR Group)		X		X		
Dietary Counseling-ALL Groups		X		X		
Meals / Snacks		X		X	X	
Follow-up Phone Call or Email				Weeks 1, 3, 5, 7	Follow-up	
Payment	\$50.00	\$350.00		\$150.00*	\$500.00	

Table 2: Laboratory

	Visit 1	Visit 2		Visit 3, 4, 5	Visit 6	
		Week 0		Weeks 2, 4, 6	Week 8	
	1 Day 3-hours	Day 1 7-9 hours	Day 2 optional	1 Day 1-hour	Day 1 7-9 hours	Day 2 optional
Laboratory	Screening	Baseline within 4 weeks of Screening Visit		Compliance (Outpatient)	Outcome	
Clinical Labs: CBC with differential, CMP, HbA1c, Phosphate, Magnesium, TSH, Liver Panel, Lipid Panel, Uric Acid, PT/INR, PTT, insulin, HIV, HBV, HCV	X					
Research Lab: Insulin	X					
Clinical Labs: CBC and PT/INR, PTT		X				
Research Labs: AD Biomarkers, Cytokines/Chemokines, Neurotrophic Factors, Exosomes, Oxidative Stress Biomarkers, gene expression and DNA methylation, WBC differential counts, β -hydroxybuterate		X				
CSF		X			X	
Research Labs: β -hydroxybuterate, gene expression and DNA methylation, WBC differential counts, plasma sample for AD Biomarkers, Cytokines/Chemokines, Neurotrophic Factors, Exosomes, Oxidative Stress Biomarkers				X		
Clinical Labs: CBC with differential, CMP, HbA1c, Phosphate, Magnesium, TSH, Liver Panel, Lipid Panel, Uric Acid, PT/INR, PTT, insulin					X	
Research Labs: AD Biomarkers, Cytokines/Chemokines, Neurotrophic Factors, Exosomes, Oxidative Stress Biomarkers, gene expression and DNA methylation, WBC differential counts, insulin, β -hydroxybuterate					X	

Amount of Blood	28 ml	168 ml	62 ml/visit	174 ml
-----------------	-------	--------	-------------	--------

4.d.2. Baseline visit

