This visit will occur within four weeks from the Screening Visit. Participants will arrive on the NIA-Clinical Research Unit after a 12-hour fast. The following procedures will be done: vital signs, anthropometric measurements (weight, waist circumference, sagittal diameter), and a blood draw for clinical labs (CBC, PT, PTT, and INR to ensure safety of the LP), urine pregnancy test (only in women who are able to become pregnant), and research labs including DNA collection (for APOE genotyping and gene expression studies). A 4-hour mixed meal tolerance test will be done. They will also have cognitive testing and will be asked to complete the Symptoms Review Questionnaire, PANAS, and RAND SF-36. A lumbar puncture (LP) will take place; up to a total of 15 mL of CSF will be collected. Participants will have a brain MRI. About 168 mL of blood will be taken during the visit. To facilitate scheduling or satisfy a given participant's request, we may split the various procedures of the Baseline Visit over two days within a week from each other.

4.d.3. 5-2 CR or control groups

At the end of the Baseline Visit, all participants will receive informational materials and one-on-one dietary counseling about "healthy living", consisting of providing and reviewing published material (by the CDC and USDA) on meal portion control, calories in common beverages, meal substitutions for controlling calorie intake, and other dietary considerations. Participants will then be randomized by study investigators into one of two groups to either 1) implement 8 weeks of 5-2 CR (cases); or 2) implement "healthy living" diet (controls).

Participants in the 5-2 group will receive all shakes (Boost®, CWI Medical) from the NIA-Clinical Research Unit.

4.d.4. Compliance visits

To assess and reinforce compliance with their respective diet, we will contact participants by phone or email (via the Secure Email & File Transfer Service: <https://secureemail.nih.gov/bds/Login.do>) at weeks 1, 3, 5, 7 and four days after the Outcome Visit. In addition, we will conduct 2, 4, and 6 week Compliance Visits. The same procedure described below will occur during each one of these.

These visits will take place during the second of the two consecutive restriction days for the 5-2 CR group or any day for the "healthy living" diet group after an 8 hour fast. A blood draw to measure β-hydroxybutyrate, vital signs and anthropometric

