measurements (weight, waist circumference, sagittal diameter) will be done. Participants will provide feedback regarding physical and psychological symptoms by completing a Symptoms Review Questionnaire and the RAND SF-36. Samples for β -hydroxybutyrate levels will be sent to Harbor Hospital Lab. In addition, a plasma sample will be sent to the NIA Core Lab for future studies. These visits will take about 1 hour.

In addition, blood will be collected for isolation of total RNA and genomic DNA for target pathways gene expression and methylation analyses, and PBMCs counts. 62 ml of blood will be collected during each one of these visits.

4.d.5. Outcome visit

The Outcome Visit will occur at the end of the 8-week period in the 5-2 CR or control group. This visit will take place during the first of the two consecutive constriction days for 5-2 CR participants or at a convenient time during the week for control participants. This visit will occur after a 12-hour fast, to ensure comparability of the mixed meal test with the Baseline Visit. The visit procedures will be similar to the Baseline Visit, including a lumbar puncture (LP) and a medical history and physical exam.

Participants will arrive on the NIA-Clinical Research Unit after a 12-hour fast. The following procedures will be done: vital signs, anthropometric measurements (weight, waist circumference, sagittal diameter), and a blood draw for clinical labs (CBC, PT, PTT, INR, CMP, lipid panel, uric acid, HgbA1c, insulin, β -hydroxybutyrate), urine pregnancy test (only in women who are able to become pregnant), and research labs including DNA collection (for gene expression studies). A 4-hour mixed meal tolerance test will be done. They will also have cognitive testing and will be asked to complete the Symptoms Review Questionnaire, PANAS, and RAND SF-36. A lumbar puncture (LP) will take place and up to a total of 15 mL of CSF will be collected. Participants will also have a brain MRI. About 174 mL of blood will be taken during each visit (including clinical and research labs). To facilitate scheduling or satisfy a given participant's request, we may split the various procedures of the Outcome Visit over two days within a week from each other.

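### The PANAS asks about mood at the moment of completion, and all scheduled post-baseline visits in the 5-2 CR arm fall on restricted days, so acute and 8-week effects on affect cannot be separated

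*Combined protocol and SAP*

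**What the plan says.** - **The form.** Attachment D heads its list of affect words with "Do you feel this way right now".
- **The hypothesis.** Section 1 (Cognition and affect) expects that participants on 8 weeks of 5-2 CR "will show improved positive over negative affect and general quality of life compared to controls".
- **Visit days, 5-2 CR arm.** For Compliance Visits, section 4.d.4 says: "These visits will take place during the second of the two consecutive restriction days". For the Outcome Visit, section 4.d.1 says that "the Outcome Visit will be timed during the second of the two CR days", but section 4.d.5 says: "This visit will take place during the first of the two consecutive constriction days".
- **Visit days, control arm.** Any day for Compliance Visits (4.d.4), and whenever convenient in the week for the Outcome Visit (4.d.5).
- **Which visits carry the PANAS.** In Table 1 the row "PANAS, RAND SF-36" is ticked at Baseline, Compliance and Outcome. Section 4.d.4 has participants at Compliance Visits "completing a Symptoms Review Questionnaire and the RAND SF-36", without the PANAS.
- **Analysis.** Section 10.a fits Group, Time (Baseline and Outcome) and their interaction to each scalar measure. Section 9 calls all secondary outcomes exploratory.

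**The concern.** The hypothesis is about mood on a regimen followed for 8 weeks. The form records mood at one moment, and in one arm that moment is tied to a particular part of the diet week. Baseline precedes the diet, so the restricted day enters only the follow-up score, and only in the 5-2 CR arm. It therefore loads on the same Group by Time term that is meant to show the effect of the diet.

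The protocol gives reason to think that the day could matter. Section 7.p expects lethargy, poor concentration and irritability in some 5-2 CR participants, and the PANAS list includes Irritable, Attentive, Alert and Active. The 5-2 CR version of the Symptoms Review Questionnaire in Attachment E asks about restricted and unrestricted days separately.

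At stake is the meaning of one preliminary estimate. Section 10.a says that the pilot is meant to supply data for later studies, and a restricted-day mood score could be carried forward as an effect of the whole regimen.

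**Working it through.** There is no figure in the plan to reproduce. Section 10.b mentions affect measures, but its informal power statement names only cytokines, ROS and BDNF. The check is therefore a comparison of passages with one piece of algebra.

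**1. What the contrast estimates.** Let D be the change in PANAS score that the diet produces on an unrestricted day at week 8, and A the additional shift on a restricted day. Changes common to both arms cancel.

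- Group by Time contrast with a momentary form on a restricted day: D + A.
- Average over the diet week, with 2 of 7 days restricted (2/7 = 28.6%): D + (2/7)A.
- Difference: A − (2/7)A = (5/7)A, or about 0.71A.

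The data give one number, D + A. With no 5-2 CR PANAS scheduled on an unrestricted diet day, D and A cannot be told apart, and section 10.a has no term for cycle day.

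**2. The two Outcome Visit texts.** If the two restricted days differ, with shifts A1 and A2, the weekly average is D + (A1 + A2)/7.

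- First day (4.d.5): the contrast is D + A1, and the distortion is (6A1 − A2)/7.
- Second day (4.d.1): the contrast is D + A2, and the distortion is (6A2 − A1)/7.

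So the meaning of the score depends on a point that the protocol leaves contradictory. On the second-day text a full restricted day precedes the form. On the first-day text only a 12-hour fast precedes arrival, as for controls and at Baseline.

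**3. The mixed meal.** Section 4.d.6 gives 5 mL/kg of a product with 710 kcal per 480 mL: 5 × 710/480 = 7.4 kcal/kg. At assumed weights of 80 and 100 kg this is 592 and 740 kcal. It passes the 480 kcal restricted-day total at 480/7.396 = 64.9 kg. The protocol does not say whether the PANAS comes before or after the meal.

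**4. Whether another instrument fills the gap.** The Symptoms Review Questionnaire uses a past-week window. Its emotion items are sadness, irritability and anxiety; energy and concentration are also rated, but no positive emotion is. It cannot yield positive relative to negative affect. The RAND SF-36 is described as a quality-of-life measure, and its form is not reproduced, so its recall window cannot be confirmed from the documents.

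**5. How many PANAS scores there are.** Table 1 and section 4.d.4 disagree about Compliance Visits. As Table 1 reads, the Symptoms Review Questionnaire is not ticked there, although the text lists it. The contrast in 10.a uses only Baseline and Outcome in either case.

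**The case against.** The strongest reply is that mood across the week is already measured. The Symptoms Review Questionnaire separates restricted from unrestricted days, controls rate the same items, and the weekly contacts in section 4.a.2 ask about mood. For negative emotions this stands, and it does more than a pooled past-week PANAS would. It leaves positive affect uncovered.

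A second reply is that a momentary form is a legitimate choice. Section 1 introduces the PANAS because the diets might cause psychological stress, and section 4.d.6 describes it as an index of emotional state. Scores taken on restricted days serve that purpose. They do not serve the directional hypothesis stated in the same part of section 1.

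Third, on the first-day text, with the form completed before the meal, the acute component could be small. That is possible, but the protocol fixes neither the day nor the order.

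A reader might also infer more than the documents support:

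- **A 3.5-fold overstatement.** The ratio of D + A to D + (2/7)A equals 7/2 = 3.5 only if D = 0, that is, if the diet does nothing on the other five days. The trial hypothesises otherwise.
- **A bias against the diet.** Section 7.p expects minor symptoms in 9–15%, during the first several weeks, whereas the contrast is at week 8. The same section cites increased self-confidence and positive mood in 32% of 5-2 CR participants. The sign of A is not known.
- **Every on-diet PANAS in this arm is on a restricted day.** This holds for the schedule only. Section 4.d.5 lets the Outcome Visit be split over two days up to a week apart, which could move the form.
- **Fasted against unfasted arms.** The 12-hour fast before the Outcome Visit applies to controls too.
- **The whole mood outcome fails.** The section 9.b item covers symptom ratings, mood and quality of life, and does not name the PANAS.

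**Conclusion.** The point holds for the PANAS alone. As scheduled, its Group by Time contrast combines any acute restricted-day effect with the 8-week effect on affect, in one arm only. The departure from a weekly average is 5A/7 if the two restricted days act alike. Neither the size nor the direction of A can be taken from the documents, and A may be close to zero.

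This rests on three assumptions: that the form is used as printed, that the Outcome Visit is not split so as to move the PANAS to another day, and that the analysis follows section 10.a. The scores remain usable as momentary mood at the visit. They neither support nor refute a statement about positive relative to negative affect over the diet as a whole. The primary outcome and the sample size are untouched. This is a minor but inexpensive correction to one exploratory secondary measure.

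**What to change.** Before the form is used, change the PANAS instruction to refer to the past week, at Baseline and at every later visit, in both arms. On the 5-2 schedule any seven-day window contains two restricted days, so the score then refers to the regimen. Record the diet-cycle day on which each form is completed.

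If participants have already been assessed, do not mix recall windows within a person. Flag those records and limit their interpretation to momentary mood on a restricted day, as confirmed by the recorded visit date.

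Separately, reconcile sections 4.d.1 and 4.d.5 on the day of the Outcome Visit, and Table 1 and section 4.d.4 on whether the PANAS is given at Compliance Visits. Changing the form settles neither.

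The cost is one line on a form and one recorded field. The downside is that scores are no longer comparable with momentary norms. A past-week answer may also still be coloured by how the participant feels on the day, which is a further reason to record the cycle day.

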ATTACHMENT E. Symptoms Review Questionnaire for 5-2 CR participants

Symptoms Review Questionnaire

Intermittent Calorie Restriction

Since **last week**, on a 1-10 scale, please rate how you felt on **NON-CR DAYS** for:

	Less	→	More								
Amount of Energy	0	1	2	3	4	5	6	7	8	9	10
Ability to Concentrate	0	1	2	3	4	5	6	7	8	9	10
Constipation	0	1	2	3	4	5	6	7	8	9	10
Headache Severity (if any)	0	1	2	3	4	5	6	7	8	9	10
Feeling Cold	0	1	2	3	4	5	6	7	8	9	10
Feeling Sad/Depressed	0	1	2	3	4	5	6	7	8	9	10
Feeling Irritable	0	1	2	3	4	5	6	7	8	9	10
Feeling Anxious	0	1	2	3	4	5	6	7	8	9	10
Feeling Hungry	0	1	2	3	4	5	6	7	8	9	10
Preoccupation with Food	0	1	2	3	4	5	6	7	8	9	10

Since **last week**, on a scale from 1-10, please rate how you felt on **CR DAYS** for:

	Less	→	More								
Amount of Energy	0	1	2	3	4	5	6	7	8	9	10
Ability to Concentrate	0	1	2	3	4	5	6	7	8	9	10
Constipation	0	1	2	3	4	5	6	7	8	9	10
Headache Severity (if any)	0	1	2	3	4	5	6	7	8	9	10
Feeling Cold	0	1	2	3	4	5	6	7	8	9	10
Feeling Sad/Depressed	0	1	2	3	4	5	6	7	8	9	10
Feeling Irritable	0	1	2	3	4	5	6	7	8	9	10
Feeling Anxious	0	1	2	3	4	5	6	7	8	9	10
Feeling Hungry	0	1	2	3	4	5	6	7	8	9	10
Preoccupation with Food	0	1	2	3	4	5	6	7	8	9	10

Have you experienced any other symptoms that you did not have before going on the diet? If so, please write down those symptoms here:

Participant ID: _____

Investigator/Staff Name: _____

Date: _____

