At the end of the Outcome visit, participants will be given an accelerometer to wear for 96 hours. They will be given instructions on how to wear the device and to mail it back to the unit via a pre-paid envelope. To ensure more accurate estimates of physical activity, participants will keep an activity log of when they sleep, exercise, or bathe.

4.d.6. Procedures

Medical history: A NIA licensed practitioner (Physician or Nurse Practitioner) will obtain standardized medical history including past medical history, current review of systems, medications and supplements, as well as family history of Alzheimer's disease and dementia.

Physical examination: Vital signs including body temperature, blood pressure, and heart rate will be obtained. A NIA licensed practitioner (Physician or Nurse Practitioner) will conduct screening head, eyes, ears, nose, and throat (HEENT), cardiovascular, respiratory, abdominal, neurological exams.

Anthropometric measurements: Height, weight, waist circumference, and sagittal diameter will be obtained with the subject in a hospital gown without shoes.

PANAS: Participants will report on Likert scales how they feel emotionally. The PANAS is a common index of emotional state.⁷¹

Symptoms Review Questionnaire: Participants will report on Likert scales their mood, level of energy, difficulty concentrating, headaches, feeling cold, constipation, negative emotions (depression, anxiety, irritability), hunger and preoccupation with food during constriction and non-constriction days for the week prior to the visit.

RAND SF-36 scale: This questionnaire gauges physical and psychosocial effects of the dietary interventions. It has been used as a quality of life assessment in our previous 5-2 CR study.⁴⁰

Screening blood tests: After a 12-hour fast, 28 mL of blood will be drawn for the following blood tests: complete metabolic panel, liver function tests, complete blood counts, PT, PTT, INR, fasting lipid panel, HbA1c, TSH, insulin, HIV, HBV, and HCV.

Screening urine toxicology screen: Urine will be collected during the screening visit for a standard toxicology screen.

Urine pregnancy test: A urine pregnancy test (only in women who are able to become pregnant) will be performed at screening and before MRI or fluoroscopic LP procedures at the Baseline and Outcome Visits.

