Participants' genetic information will be kept confidential to the extent possible. The results of participants' genetic testing will be kept in a locked and secured manner at the NIH. Genetic information will not be part of participants' medical record. Genetic information about participants will not be revealed to others, including their relatives, without participants' written permission. Similarly, participants will not receive information about other family members.

Problems, such as with insurance or employment discrimination, may occur if participants disclose information about themselves or agree to have their research records released. We will not release any information about participants or their families to any physician, insurance company or employer unless you sign a document allowing release of the information.

Further discussion can be found under Section "20. Confidentiality" on pages 51-52.

7.o. Accelerometry: The accelerometer has no risks associated with its use and causes minimal inconvenience.

7.p. 5-2 CR/Control Diet: Overall, a minority of participants (9-15%) is expected to develop minor physical and psychological AEs during the first several weeks of 5-2 CR. Such AEs include lethargy, feeling cold, difficulty concentrating, and irritability. Participants may experience minor psychological symptoms such as feeling hungry (leading to preoccupation with food), lack of concentration, bad temper and irritability. The Harvie et al. study is especially important because our study design is similar to it. In the Harvie et al. study, a small number of participants on the 5-2 CR regimen (8%) reported physical symptoms including lack of energy, headaches, feeling cold, and constipation. Minor psychological symptoms included lack of concentration, bad temper, and a preoccupation with food among 15% of the 5-2 CR group. These adverse effects abated after cessation of CR. Conversely, 6% of 5-2 CR participants reported better health and increased energy.⁴⁰ Furthermore, 32% of 5-2 CR had increased self-confidence and positive mood. To minimize these risks, participants will be told ahead of time about potential side effects. During Compliance Visits, we will give participants the opportunity to discuss and will offer encouragement that may ameliorate minor psychological symptoms.

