ATTACHMENT E. Symptoms Review Questionnaire for “Healthy Living Diet” participants

Symptoms Review Questionnaire

Healthy Living Diet

Since **last week**, on a scale from 1-10, please rate these items for how you felt

	Less	→	More
Amount of Energy	0	1	2 3 4 5 6 7 8 9 10
Ability to Concentrate	0	1	2 3 4 5 6 7 8 9 10
Constipation	0	1	2 3 4 5 6 7 8 9 10
Headache Severity (if any)	0	1	2 3 4 5 6 7 8 9 10
Feeling Cold	0	1	2 3 4 5 6 7 8 9 10
Feeling Sad/Depressed	0	1	2 3 4 5 6 7 8 9 10
Feeling Irritable	0	1	2 3 4 5 6 7 8 9 10
Feeling Anxious	0	1	2 3 4 5 6 7 8 9 10
Feeling Hungry	0	1	2 3 4 5 6 7 8 9 10
Preoccupation with Food	0	1	2 3 4 5 6 7 8 9 10

Have you experienced any other symptoms that you did not have before going on the diet? If so, please write down those symptoms here:

Participant ID: _____

Investigator/Staff Name: _____

Date: _____

26. Consent forms

Please see attached consent forms for healthy adult volunteers.

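### Both symptom forms instruct a 1-10 rating but print 0-10 with no labelled zero, and the concentration item runs opposite to the construct named in aim 9 and section 4.d.6

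*Combined protocol and SAP*

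**What the plan says.** The Symptoms Review Questionnaire in Attachment E has two versions.

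- **5-2 CR form.** It has two grids. The one for non-CR days asks participants "on a 1-10 scale, please rate how you felt on" those days. The one for CR days asks them "on a scale from 1-10, please rate how you felt on" those days.
- **Control form.** It has one grid and asks participants "on a scale from 1-10, please rate these items for how you felt".

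Each grid lists the same ten items. Every item has printed options from 0 to 10, for example "Constipation 0 1 2 3 4 5 6 7 8 9 10". The column headings give only Less and More, and no number is labelled as absence of the symptom.

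The second item on both forms is "Ability to Concentrate". The description of this questionnaire in section 4.d.6 says otherwise: "Participants will report on Likert scales their mood, level of energy, difficulty concentrating, headaches, feeling cold, constipation". Specific aim 9 in section 2 also lists difficulty concentrating among its topics. Section 7.p treats it as an expected minor effect of the diet: "Such AEs include lethargy, feeling cold, difficulty concentrating, and irritability".

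Section 9.b lists ratings of symptoms that can occur with 5-2 CR as a secondary outcome, and section 9 declares all secondary outcomes exploratory. Section 10.a plans a separate mixed model for each secondary scalar measure, with one-tailed tests. Section 8.a names this questionnaire as one route for eliciting adverse events. Neither document section nor form gives a scoring key, a rule for 0 versus 1, or a reversal of the concentration item.

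**The concern.** There are two defects in the same participant-facing form.

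The first is the range. Someone with no constipation who follows the instruction circles 1. Someone who follows the printed row circles 0. Both answers are valid readings of the form, so one state has two codes.

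The second is direction. On a Less-to-More axis, a high rating for ability is good and a high rating for difficulty is bad. The protocol describes the item one way and the form asks it the other way. Because section 10.a calls for one-tailed tests, the direction of each score should be fixed before analysis. For this item the documents point both ways.

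At stake are the precision of the symptom ratings, and the correct reading of one item that section 7.p expects the diet may worsen.

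**Working it through.** The plan gives no figure to reproduce here. The check compares the texts and adds simple counting.

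**1. Range.** The instruction in all three grids allows 1 to 10, which is 10 values. The printed rows allow 0 to 10, which is 11 values. With 10 items in each of 3 grids, 10 × 3 = 30 rows carry the conflict.

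**2. Items affected at the low end.** Of the ten items, eight are symptoms whose low end means absence: constipation, headache, feeling cold, sad or depressed, irritable, anxious, hungry, and preoccupied with food. The other two, energy and concentration, have their worst state at the low end, so the two-codes problem for absence does not apply to them. 10 − 2 = 8.

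**3. Size at one visit.** Assume that a share q of symptom-free respondents circle 1 and the rest circle 0. Their mean on that item is q × 1 + (1 − q) × 0 = q. As q runs from 0 to 1, the mean runs from 0 to 1 point. The documents do not give q.

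**4. Size in a change score.** Take a person who is symptom-free at both visits.

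| Baseline code | Outcome code | Recorded change |
|---|---|---|
| 0 | 0 | 0 |
| 1 | 1 | 0 |
| 0 | 1 | +1 |
| 1 | 0 | −1 |

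A consistent respondent shows no spurious change. A respondent who switches codes shows one point in either direction. The lower limit of the effect is therefore zero and the upper limit is one point per item.

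**5. Arms.** The instruction and the printed range conflict in the same way on the 5-2 CR form and the control form. The conflict therefore adds noise and does not by itself favour an arm.

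**6. Direction.**

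| Place | Construct | Higher rating means |
|---|---|---|
| Attachment E, both forms | Ability to concentrate | Better |
| Section 4.d.6, description of this form | Difficulty concentrating | Worse |
| Section 2, aim 9 | Difficulty concentrating | Worse |

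Concentration is the only item whose direction is reversed. The energy item matches the level of energy named in section 4.d.6.

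**7. The two defects interact.** A reversal that keeps the score within its own range is 10 − x on a 0-10 scale and 11 − x on a 1-10 scale. The two differ by one point for the same x, so the range has to be settled before a reversal rule can be written.

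**The case against.** The strongest reply is that neither mismatch does measurable harm as the plan stands, and much of it is right.

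- **Sign of the concentration result.** A reader might infer that a worsening under 5-2 CR will be reported as an improvement. The documents do not say so. Section 10.a analyses each measure separately, and no symptom total is defined in which directions would mix. Reported under its own label, a fall in ability reads correctly as worsening. A reversed conclusion requires someone to rename the column as difficulty and leave the numbers alone.
- **Loss of precision.** A reader might also put a percentage on the added variance. The documents give no standard deviation of change, no share of participants at the lowest rating and no rate of switching between codes. Any such percentage would have to assume all three, and it falls to zero if people answer consistently. It is also doubtful that most people sit at the floor for hunger or preoccupation with food, especially on CR days.
- **Safety.** Detection of concentration problems does not rest on this rating. The weekly contacts in section 4.a.2 ask about difficulty concentrating directly, although they are calls or e-mails and not this form. Section 8.a also seeks adverse events at every contact and through history and examination, and both forms end with a free-text symptom question.
- **Aim 9 and section 9.b.** Aim 9 is a list of topics in mixed directions, and section 9.b names no individual items. The direct contradiction is between section 4.d.6 and the form it describes.

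What remains is that the form contradicts itself on its range, the protocol contradicts the form on one item, and no scoring rule resolves either.

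**Conclusion.** The point holds as a minor wording defect in the instrument. For the eight symptom items, the lowest rating has two possible codes. The effect is between zero and one point per item, it is present equally in both forms, and it vanishes from change scores when respondents are consistent. That two codes stand for no symptom is an inference, though a sound one: the forms never label such a value.

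The concentration item runs opposite to the construct in section 4.d.6 and aim 9. The result would be misread only if it were reported under the protocol's term without reversal, and it can be recovered from the raw ratings. The outcome is exploratory and secondary, so the primary analysis is untouched. The correction is worth making because it is nearly free and because one-tailed testing needs the direction of each score settled in advance.

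**What to change.** **Range.** Change the instruction to 0-10 on all three grids of Attachment E. Label the endpoints: 0 as none for the symptom items, and separate anchors for energy and concentration, whose low end is the worst state.

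**Concentration.** Choose one of three:

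1. Reword the item on both forms as difficulty concentrating, so that it becomes a symptom item with 0 as none.
2. Change section 4.d.6 and aim 9 to refer to ability to concentrate.
3. State in section 10.a that the analysed score is 10 minus the rating, which presupposes the 0-10 range.

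**Cost.** This means edits to two forms and, depending on the option, one or two sentences of protocol text. Forms already collected under the 1-10 instruction need a version flag, because their zeros and ones cannot be recoded with certainty. Options 2 and 3 leave the concentration item as participants have seen it. Option 1 changes it, so earlier answers would have to be reversed before pooling.
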